1 ADMINISTRATIVE INFORMATION

1.1 Registration of observational research

This trial has been submitted for registration on ANZCTR (ACTRN Request Number [382577](#); submitted [27 April 2024](#)). Universal Trial Number U1111-1268-7555.

1.3 Expected duration of study

It is expected that 550 infants from 5 Victorian Tertiary level NICUs across Victoria will be recruited over a 3-year period from the date of when the first infant is enrolled into the study. Study infants will remain on-study from date of enrolment until 2 years corrected age. The study is expected to be completed when the last study child has completed a 2-year assessment (± 3 -month window for assessment scheduling).

1.5 Source of funding

This study is funded by a NHMRC Clinical Trials and Cohorts Scheme Grant (GNT2024039).

1.6 Stakeholder involvement

Consumer input was sought in the study development from [name] and [name] from the ByBoet Foundation, who are also listed as Associate Investigators on the original BLUEPRINT NHMRC grant application. Both will have ongoing involvement in study conduct and knowledge dissemination and be members of the Study Steering Committee. Consumers' top priorities for research regularly include improving respiratory outcomes for preterm infants, including in the recent James Lind Alliance Priority Setting Partnership Project for the most preterm infants (MCRI co-lead).

2 INTRODUCTION AND BACKGROUND

2.1 Background and rationale

Globally, 15 million babies are born preterm each year, and 1 million die.(1) Respiratory disease is the greatest cause of illness for these infants;(2) almost 75% born before 32 weeks' gestation receive assisted respiratory support. However, surviving to discharge home is not the endpoint for this respiratory burden. Ventilation of the underdeveloped lung is a double-edged sword; necessary for survival but risk long-term injury to the lungs.(2) Despite 40 years of advances in respiratory support, many preterm infants develop early lung injury that eventually leads to chronic lung disease (CLD) throughout infancy, childhood and in adult life. This burden is increasing.(3, 4)

The accepted measure of in-hospital respiratory morbidity, bronchopulmonary dysplasia (BPD) diagnosed at 36 weeks' postmenstrual age (PMA)(5), does not reliably predict respiratory complications in later life and has often been conflated to represent CLD status.(6) Irrespective of BPD status, childhood respiratory function in preterm survivors is now worse than 25 years ago. Abnormal childhood respiratory function is associated with adult obstructive CLD and deteriorating lung function.(7, 8) Necessitating urgent re-evaluation of how early preterm respiratory disease is defined, identified and managed, in order to reduce the ensuing burden on infants, families and health services.

Avoiding the trajectory towards CLD in later life requires modulation of the early life events that initiate the lung injury/inflammation cascade at and shortly after birth (**Figure 2a**). Currently, these events are defined from crude measures that poorly categorise the complexity of prematurity and NICU management. To provide the right lung protective treatment, at the right time, clinicians need precise guidance to make decisions that avoid or modify the initial disease process.

This study aims to bring together the tertiary-level NICUs in Victoria to:

1. Define early-life respiratory phenotypes in preterm infants,
2. Link these phenotypes to medium (in-hospital) and long-term respiratory outcomes, specifically BPD and respiratory health at 1 and 2 years of corrected age, and
3. Integrate protein biomarkers, lung imaging and clinical tools to define the continuum of modifiable mechanical-molecular-clinical interactions occurring in early preterm life.

[figure not shown]

Figure 2a Preterm respiratory health is determined by a cascade of differing early life experiences that alter the trajectory of lung growth during childhood and risk of chronic lung disease in later life. Developing meaningful long-term benefits requires targeted disease modifying therapies using a multidimensional approach.

The specific purpose of this prospective observational cohort study is to:

1) Develop the first functional classification of preterm respiratory disease: Comprehensively define the preterm respiratory phenotype in the first 7 days of life using a range of biomarkers, including circulating proteins, imaging, and clinical information, and delineating the influence of gestation, maternal factors, and clinical interventions on marker expression.

2) Accurately predict BPD: Determine how specific early preterm phenotypes relate to a diagnosis of BPD and develop a predictive modelling tool for the early diagnosis of BPD that can be implemented in daily clinical practice. By doing so, we hope to delineate the first set of practical repeatable measures that clinicians can use to predict the trajectory towards BPD, compare therapeutic benefits and potentially inform decisions that will improve NICU care.

3) Improve our understanding of the longer-term implications of early respiratory disease: Characterise the respiratory health of preterm infants in the first 2 years after birth. By doing so, defining the relationship between initial respiratory phenotype, BPD status and early childhood respiratory health. Providing a robust approach to continually assess infant lung function and lung growth from the NICU into childhood that may offer better utility for determining long-term respiratory risk from prematurity and provide parents with relevant expectations regarding their child's health.

Together, our study aims will address the key knowledge gaps identified in the *'American Thoracic Society Statement on the Care of the Child with Chronic Lung Disease of Infancy and Childhood'*:

- What are the best methods to describe BPD?
- What is the natural history of lung function changes in chronic lung disease of infancy?
- What is the relative importance of early injury events on chronic lung disease in childhood?

Achieving these aims will represent a major and enduring conceptual shift in the approach to neonatal lung protection relevant to all modern NICU care worldwide.

Defining the early origins of BPD progression is essential to improving outcomes

Reducing the rate of BPD continues to challenge neonatologists, with few therapies demonstrating benefit to date.(2, 9) BPD results from injury initiated in the early neonatal period and is exacerbated by other morbidities such as sepsis. Currently, BPD is diagnosed at 36 weeks' PMA,(2, 10-12) well after the initiating events. This late diagnosis limits the application of interventions designed to alter respiratory outcomes.(9) Several clinical factors (e.g. gestation, sex, chorioamnionitis, duration of mechanical ventilation and supplemental oxygen needs) are associated with BPD.(2) However, none alone or in combination have shown to accurately predict the risk.(9, 11) The reasons for this inaccuracy may lie in the use of measures that are too crude to allow prediction of this complex disease. This is perpetuated by a 'one-size-fits-all' approach to applying various respiratory therapies available in the NICU (e.g. continuous positive applied pressure, high-flow nasal cannula, intubation).(2) Therefore, to progress and reliably predict respiratory risks, there is a pressing need to identify these complex early phenotypes at a biological systems level. Such information will not only serve as targets for interventions aimed at ameliorating lung injury, but to also guide respiratory decisions in the crucial period shortly after birth when strategies to prevent BPD may have the most benefit.

BPD is the result of a multi-modal inflammatory cascade of events but is defined purely on clinical status. Our pilot work suggests that the inclusion of both protein and lung function (imaging) measures (with clinical data) in the first 7 days can differentiate respiratory phenotypes that improve the accuracy of BPD prediction. This is the critical first step in implementing stratified lung protective respiratory care based on evidence before the initial injury-inflammation cascade becomes entrenched.

Defining the landscape of early preterm life: many phenotypes, many choices, many outcomes

Survival following birth before 32 weeks' gestation requires the lung to ventilate whilst in a saccular or canalicular stage of development, before the formation of alveoli and production of surfactant. Broadly, preterm lung injury is due to multiple injurious stimuli applied to the structurally immature and surfactant deficient lung in this early postnatal period. Maternal (e.g. chorioamnionitis), infant (e.g. weight, sex, gestation) and immune factors alter the likelihood of lung injury.(2, 13) Hence, the development of preterm lung injury is a multi-factorial process; a complex interplay between numerous pathophysiological and patient-derived factors. The injury process continues to evolve, influenced by treatment choices in the NICU (e.g. intubation, surfactant therapy). However, as we have shown, the pathological process (biotrauma) is unique to each infant but can also be defined using a combination of molecular (proteomics), imaging and clinical data.

Our Neonatal Proteomics program has applied advanced mass spectrometry to identify the mediators, pathways and mechanisms that define the biotrauma response that occurs within the preterm lung.(14-16) Using our bioinformatics approach,(14, 16) we have determined the molecular events associated with specific respiratory strategies at different gestations.(14, 17, 18) Importantly, because our quantitative proteome approach is comprehensive (analysis of high and low abundant protein species) and unbiased (untargeted), we have identified new regulators and pathways related to specific clinical interactions resulting in injury (and vice versa) not detected using traditional methods.(16)

Measuring lung function at a resolution that links injurious lung states (for example atelectasis and volutrauma) with clinical treatments has previously been impossible in infants. We have utilised two high-resolution bedside imaging techniques in the NICU; lung ultrasound (LUS) and electrical impedance tomography (EIT).(19-21) Both provide radiation-free, repeatable, detailed breath-by-breath imaging of aeration. EIT also images regional lung ventilation and mechanics. We have shown that LUS and EIT assessments of ventilation in early preterm life predicts BPD risk,(20) and can direct clinical respiratory decision making in the NICU.(22, 23) We have also shown that standard EIT measures

correlate with the molecular and proteome changes occurring within the preterm lung associated with injurious and protective respiratory therapies.(18, 23) Importantly, both EIT and LUS can be repeated through childhood.

Complex disease trajectories require comprehensive mapping techniques to characterise them

Addressing the complexity of early lung injury requires a sophisticated, multi-modal mapping approach. Biomarker data are captured at the cellular level (mass spectrometry of plasma) and system level (EIT and LUS) and then integrated with clinical information. We will use bioinformatics techniques to map these interactions. By doing so, we hope the methods we develop in this study may 1) improve our understanding of the best timing for interventions, 2) identify new therapeutic options and tools for defining an intervention's success, failure and/or suitability, and 3) increase our understanding of the impact of secondary perinatal and maternal factors on preterm lung injury. A similar approach has been successfully employed in paediatric and adult acute respiratory distress syndrome (a functionally similar condition to preterm acute lung disease).(24, 25)

Is it time to re-think our reliance on BPD to define preterm respiratory outcomes?

The accepted definition of BPD has changed as neonatal medicine has evolved. Originally a pathological definition, the current definition is based upon a level of respiratory support and oxygen dependency at 36 weeks' PMA.(2, 5, 11, 12) No definition is ideal, and all are based upon a single trait (e.g. respiratory support) that narrows categorisation and ignores the multi-modal impact of preterm birth on the lung.(11, 12, 26) Most BPD definitions were developed in an era in which babies born at 22- and 23-weeks' gestation rarely survived. As BPD remains the primary outcome measure for large neonatal trials, this fundamental problem has arguably limited the development of new respiratory treatments. More concerningly, childhood respiratory function does not always relate to BPD diagnosis.(3, 4) Poor compliance with traditional pulmonary function tests in early childhood precludes reliable assessment of respiratory function. This creates a period of clinical and parental uncertainty during the early years of childhood. Our study standardises lung function assessments before and after NICU care to better understand how biological and physiological events in the early newborn period shape the trajectory of lung growth and health outcomes in later life. This may aid in understanding important respiratory factors not currently recognised using current BPD diagnostic criteria, and provide the missing link between BPD, as currently defined, and impaired respiratory function in childhood.

Summary of BLUEPRINT Study Design

The BLUEPRINT study is a longitudinal prospective observational study aiming to recruit preterm infants from a maximum of 5 tertiary NICUs in Victoria (Australia) and follow them from the early NICU experience (24 hours to Day 14), through to 36 weeks' PMA or discharge and then an annual review at 1 and 2 years corrected age to assess respiratory health.

Detailed clinical data on the antenatal, delivery and initial NICU course (24-, 48-, 72-hours, 7 and 14 days) will be collected, focusing on respiratory care and complications of prematurity. BPD status will be collected at 36 weeks' PMA, as well as data on known complications of preterm birth and NICU management at discharge.

Blood samples will be collected at approximately 72 hours and Day 7 for mass spectrometry analysis of the plasma proteome.

LUS and EIT imaging will be performed at 24, 72 hours and Day 7, and then repeated at Days 14 and 28, and 36-weeks' PMA.

Families who agree to follow-up after hospital discharge will be asked to attend the MCRI research clinic for assessment of respiratory health (clinical assessment and standardised questionnaire) at 1 and 2 years corrected age. LUS and EIT imaging will be repeated at these appointments.

2.2 Definitions

The following definitions are applicable to this study:

Phenotype = any observable characteristic or trait of a disease, such as the clinical presentation of an individual. There is no implication of a mechanism.

Endotype = an endotype is defined by a distinct function or pathobiological mechanisms that manifest in or are exhibited by a phenotype or cluster of phenotypes.

An early life preterm respiratory-specific endotype may present with phenotypic clusters of disease. Preterm respiratory-specific endotypes can be specific to a particular time-point and can also be defined longitudinally over the first 2 years after birth (corrected for gestation).

2.3 Study aim(s)

The aim of this study is to describe the respiratory phenotypes and endotypes of infants born preterm in early-postnatal life, who are managed in the NICU using standard respiratory support practices.

By doing so, we aim to:

- 1) Define the clinical, lung function and molecular characteristics of early respiratory disease in preterm infants.
- 2) Determine the relationship between these endotype characteristics and later BPD status.
- 3) Determine the relationship between these endotypes and respiratory health at 1 and 2 years corrected age.
- 4) Develop predictive modelling tools for the early diagnosis of BPD and respiratory health in the first 2 years after birth.

3 STUDY OBJECTIVES AND OUTCOMES

3.1 Objectives

3.1.1 Primary objective

The primary objective of the BLUEPRINT study is to comprehensively define the respiratory phenotype and endotypes using observations from the first 7 days after birth in preterm infants born between 22+0 and 31+6 weeks' gestation.

3.1.2 Secondary objectives

The secondary objectives of this study are:

1. To compare the respiratory endotypes associated with different respiratory outcomes using observational data at 72 hours after birth in preterm infants born between 22+0 and 31+6 weeks' gestation.
2. To develop the first functional classification of preterm respiratory disease using a combination of clinical, lung imaging and molecular biomarkers.

3. Determine how specific early preterm endotypes relate to a diagnosis of BPD to develop a predictive modelling tool for the early diagnosis of BPD that can be used in everyday clinical practice.
4. Determine how specific early preterm endotypes relate to outcomes of the primary NICU admission, including duration of invasive mechanical ventilation and supplementary oxygen support, mortality, need for supplementary oxygen at discharge home.
5. To characterise the respiratory health of preterm infants in the first 2 years (corrected) after birth.
6. To characterise overall childhood health of preterm infants in the first 2 years (corrected) after birth.
7. To determine the relationship between initial respiratory endotype, BPD status and early childhood respiratory health at 1 and 2 years of corrected age.
8. To determine the performance of early life endotypes against a 36-week diagnosis of BPD in predicting respiratory outcomes at 1 and 2 years of corrected age.
9. To determine the relationship between LUS-derived measures of respiratory status at 14 and 28 days after birth and BPD status.
10. To determine the relationship between EIT-derived measures of respiratory status at 14 and 28 days after birth and BPD status.
11. To use plasma proteomics to identify proteins whose expression is altered in the first 7 days of life in infants who later are diagnosed with BPD.
12. To use plasma proteomics to identify expression pathways associated with specific preterm respiratory endotypes in samples obtained at 72 hours and 7 days post-birth.
13. To determine the impact of clinical interventions on the development of the respiratory phenotype.

3.1.3 Exploratory objectives

The BLUEPRINT study aims to explore the role of precision medicine and prediction modelling in neonatal critical care, and the development of new approaches to understanding long-term respiratory impacts of preterm birth that may address some of the limitations of the use of BPD and the lack of sound methods of defining respiratory health in infancy.

There are some important exploratory objectives that may arise from this study. Specifically:

1. Whether respiratory health and complications of preterm birth can be better defined using an alternative set of diagnostic criteria for BPD that better reflect functional respiratory health and clinical events in the NICU, or a new entity entirely based upon new biomarkers.
2. Whether plasma protein biomarkers can improve the ability to define respiratory trajectory following preterm birth, specifically with relation to response to respiratory care and early identification of complications of preterm birth.

3. Whether LUS and EIT biomarkers can improve the ability to define respiratory trajectory following preterm birth, specifically with relation to type of respiratory care and complications of NICU and preterm birth.
4. Whether heterogeneity of ventilation is a predictor of later BPD and respiratory health at 1 and 2 years (corrected).
5. Whether a series of measures or definition of respiratory health at 1 and 2 years can be developed that would provide a more meaningful representation of the respiratory impact of preterm birth than the diagnosis of BPD.
6. Whether the inclusion of unsupervised plasma proteomics and LUS and EIT may identify novel treatments via identification of previously unexplored concepts and/or molecules that influence preterm respiratory outcomes.
7. Whether the comprehensive clinical, imaging and protein datasets generated may allow for a better understanding of the extrapulmonary impact of preterm respiratory disease.
8. To determine the relationship between maternal and fetal characteristics and plasma protein abundance at 72 hours and 7 days post-birth.

3.2 Outcomes

Table 3a defines the outcomes measures in relation to objectives and confounders.

Table 3a Listing objectives, exposure, outcomes and outcome measures, and confounders

PRIMARY OBJECTIVE
To comprehensively define the respiratory phenotype in the first 7 days after birth of preterm infants born between 22+0 and 31+6 weeks' gestation.

Exposure:
 
Day 7 after birth.

Outcome & outcome measure:
 
Functional endotypes defined from clinical, plasma protein and lung imaging measures using latent class analysis followed by external validation via group-based trajectory modelling.

Confounding factors:
 
Maternal and antenatal factors and management, clinical decisions regarding respiratory support (site and clinician differences in guidelines and management), preterm non-respiratory complications (such as infection, neurological disease, necrotising enterocolitis).

SECONDARY OBJECTIVES
To compare the respiratory endotypes associated with different respiratory outcomes using observational data at 72 hours after birth in preterm infants born between 22+0 and 31+6 weeks' gestation.

Outcome & outcome measure
 
Functional endotypes defined from clinical, plasma protein and lung imaging measures using latent class analysis (LCA) followed by external validation via group-based trajectory modelling.

To develop the first functional classification of preterm respiratory disease using a combination of clinical, lung imaging and molecular biomarkers.

Outcome & outcome measure
 
Temporally specific respiratory phenotypes derived from longitudinal latent class analysis of clinical, lung imaging and molecular biomarker data from all time points of the study.

To determine how specific early preterm phenotypes relate to a diagnosis of BPD and use this delineation to develop a predictive modelling tool for the early diagnosis of BPD.

Outcome & outcome measure

BPD status at 36 weeks' corrected PMA using Walsh Definition and Jensen Grade of Severity and functional endotypes determined above.
SECONDARY OBJECTIVES cont.
To determine how specific early preterm endotypes relate to outcomes of the primary NICU admission, including duration of invasive mechanical ventilation and supplementary oxygen support, mortality, need for supplementary oxygen at discharge home.
Outcome & outcome measure
Duration of invasive mechanical ventilation and supplementary oxygen support, mortality and need for supplementary oxygen at discharge home as independent outcomes and functional endotypes determined above.
To characterise the respiratory health of preterm infants in the first 2 years (corrected) after birth.
Outcome & outcome measure
Respiratory health status questionnaire, gravity-dependent and right-left lung centre of ventilation and homogeneity index (EIT*) and LUS* score (LUSS) at 1 and 2 years corrected age.
To characterise overall childhood health of preterm infants in the first 2 years (corrected) after birth.
Outcome & outcome measure
General health status defined by growth parameters and medical history since discharge and development (PARCA-R) questionnaires.
To determine the relationship between initial respiratory phenotype, BPD status and early childhood respiratory health.
Outcome & outcome measure
Respiratory phenotype at 72 hours and Day 7, BPD status and severity grade and Respiratory health outcomes at 1 and 2 years corrected age.
To determine the performance of early life endotypes against a 36-week diagnosis of BPD in predicting respiratory outcomes at 1 and 2 years of corrected age.
Outcome & outcome measure
BPD status at 36 weeks' corrected PMA using Walsh Definition and Jensen Grade of Severity, respiratory health at 1 and 2 years corrected age and functional endotypes determined above.
To determine the relationship between LUSS-derived measures* of respiratory status at 14 and 28 days after birth and BPD status.
Outcome & outcome measure

The accuracy of the blindly calculated LUS score proposed by Brat et al(27) in predicting a final diagnosis of BPD at 36 weeks (Yes/No). This score will be used as the primary lung ultrasound score incorporated into the predictive model.
To determine the relationship between EIT-derived measures of respiratory status at 14 and 28 days after birth and BPD status.

Outcome & outcome measure
 
Gravity-dependent and right-left lung centre of ventilation and homogeneity index (EIT*) at 14 and 28 days after birth.

To use plasma proteomics to identify proteins whose expression is altered in the first 7 days of life in infants who later are diagnosed with BPD.

Outcome & outcome measure
 
Difference in plasma protein abundance at 72 hours and 7 days post-birth between infants with and without BPD.

To use plasma proteomics of samples obtained at 72 hours and 7 days post-birth to identify pathways whose expression is associated with specific preterm respiratory endotypes.

Outcome & outcome measure
 
Bioinformatic analysis to determine increased association of endotype-associated proteins with specific pathways and biological processes.

To determine the impact of clinical interventions on the development of the respiratory phenotype.

Outcome & outcome measure
 
Sub-analysis will be performed to identify the impact of clinical interventions on plasma proteome composition using clustering methods, including hierarchal clustering, principal component analysis and k-means clustering and one-way analysis of variance (ANOVA).
 
Clinical interventions will include (but not limited to) surfactant administration, mode of support, ventilator settings, corticosteroid administration, blood transfusion and duration of invasive ventilation.

*Measures to define ventilation and aeration patterns using EIT and LUS are based upon existing guidelines.(23) Both technologies are likely to generate new outcome measures and scoring systems for global and regional ventilation, aeration and lung mechanics during the study period. These outcome measures may be added if 1) they can be extracted from raw imaging data acquired at Scheduled Assessments and 2) they have been considered valid measures in international standards.

Outcome measures are further detailed in Section 6.

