6.2.4 Lung Function Assessments: Lung Imaging

A LUS and EIT manual of procedures and operations will be developed for each Site. LUS and EIT imaging will be conducted at 72 hours and on Day 7 after birth (with a ± 12-hour window) at a time deemed clinically suitable by the bedside nursing and/or medical team. Where possible, both imaging modalities will be performed concurrently. If clinically appropriate to do so, EIT and LUS images will also be collected at 24 and 48 hours after birth as additional data. Data on the tolerance of lung imaging modalities will be documented. Factoring in time to allow the infant to settle between care, any position changes and image acquisition, between 30-60 minutes is anticipated to record all imaging required at each visit.

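### Table 3a promises external validation of the Day 7 and 72-hour endotypes by group-based trajectory modelling, but the protocol names no independent data in which to do it

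*Protocol*

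**What the plan says.** In Table 3a (section 3.2) the primary outcome is a set of functional endotypes obtained from clinical, plasma protein and imaging measures, "using latent class analysis followed by external validation via group-based trajectory modelling". The exposure for this row is given as "Day 7 after birth".

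The first secondary objective compares endotypes "using observational data at 72 hours after birth in preterm infants born between 22+0 and 31+6 weeks' gestation". Its Table 3a row has the same validation step: "using latent class analysis (LCA) followed by external validation via group-based trajectory modelling".

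The inputs are scheduled as follows.

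- **Plasma:** "Blood samples will be collected at approximately 72 hours and Day 7 for mass spectrometry analysis of the plasma proteome" (section 2.1, study design summary).
- **Imaging:** "LUS and EIT imaging will be conducted at 72 hours and on Day 7 after birth", and "If clinically appropriate to do so, EIT and LUS images will also be collected at 24 and 48 hours after birth as additional data" (section 6.2.4). Table 5a and section 6.2.2 also mark the 24- and 48-hour scans as optional.
- **Clinical data:** collected at birth, 24, 48 and 72 hours and Day 7 (Table 5a, section 6.2.3).

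The synopsis gives the primary outcome as cross-sectional and longitudinal latent class analysis. It mentions neither trajectory modelling nor external validation.

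**The concern.** External validation has a specific meaning: the classes are tested in data that did not produce them. Group-based trajectory modelling is itself a finite-mixture clustering method. Applied to the cohort that generated the latent classes, it can show that two views of one sample agree. It cannot show that the classes would appear in other infants or other units.

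The claim sits in the definition of the primary outcome, and later Table 3a rows (BPD, NICU outcomes, performance against BPD at 1 and 2 years) reuse these endotypes. If the wording carries into the report, classes from at most five NICUs in one state would be presented as more general than the design can show. The primary row itself lists differences in practice between sites and clinicians as a confounder. Classes formed by those differences could agree with trajectories in the same infants, because both carry the same site effects.

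**Working it through.** **1. Is there any independent data source?** The relevant sections, side by side:

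- Synopsis, sections 1.3 and 4.2: one cohort of 550 infants, up to five Victorian NICUs.
- Section 6.2.5: residual plasma is kept for possible later marker validation, but it comes from these same infants.
- Section 11.2: the only model validation described is internal (cross-validation and bootstrapping). It concerns the prediction models, and the logistic and machine-learning models are compared on the same data.

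No second cohort, held-out site or temporal split is named. Infants designated as external: 0 of 550. That the trajectories use the study's own infants is an inference from this absence; the protocol does not say so.

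**2. How many time points does each input supply?** With T time points the highest polynomial a trajectory can take is of degree T − 1. One point gives a level only. Two give a straight line whose shape cannot be checked. Three are the minimum for any curvature. Counts from Table 5a:

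| Input | Up to 72 h | Up to Day 7 | Whole study |
|---|---|---|---|
| Plasma | 1 | 2 | 2 |
| Imaging, required | 1 | 2 | 7 |
| Imaging, optional extra | 2 | 2 | 2 |
| Clinical, birth included | 4 | 5 | 9 |

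- **Plasma:** degree 1 − 1 = 0 up to 72 hours (no trajectory) and 2 − 1 = 1 up to Day 7 (a straight line at most).
- **Imaging:** the required scans give the same degrees. With both optional scans there would be 1 + 2 = 3 sessions by 72 hours and 2 + 2 = 4 by Day 7. Consent is allowed up to 72 hours, so infants consented after 48 hours cannot have the early scans.
- **Clinical:** three points by 72 hours without the birth record, four with it. A trajectory is feasible.

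**3. Is the imaging count stable across the protocol?** No. The synopsis lists 48 and 72 hours and Day 7. The design summary in section 2.1 lists 24 and 72 hours and Day 7. Neither marks the early scan as optional. On either text there are two sessions by 72 hours and three by Day 7.

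**4. Do the sections agree on the method?** Table 3a requires group-based trajectory modelling. The synopsis outcome and the phenotyping methods in section 11.2 do not mention it. The nearest phrase in section 11.2 concerns growth curves as a way to code repeated predictors in the prediction models.

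**5. Does this touch the sample size?** No. The protocol's only calculation is for the BPD prediction model: 500, 550 and 600 infants for 10, 11 and 12 predictors. Recomputing with prevalence 0.69, C-index 0.75 and an assumed shrinkage target of 0.90 gives 503, 553 and 603. The stated figures reproduce and are not in question here.

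**The case against.** The strongest defence is that Table 3a does not say which series or period the trajectories will use. Required imaging runs to two years, and clinical data run to the end of the NICU stay. Classes formed at 72 hours or Day 7 could be compared with later trajectories in measurements that did not form them. A reader might infer from Table 3a that the method simply re-clusters the same data; the text does not establish that. This part of the defence stands. Such a comparison would be a useful test of construct validity, but in the same infants and units it would still not be external validation.

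Two other strong readings are tempting. One is that the primary endotypes rest on a single 72-hour measurement. They do not: the primary row runs to Day 7, with two plasma samples and at least two imaging sessions. The single-measurement limit belongs to the 72-hour secondary row. The other is that trajectory modelling cannot be run for that row at all. The protocol does not support this either: the limit is strict only for plasma, depends on the optional scans for imaging, and does not apply to clinical data.

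It can also be said that a separate SAP will hold the detail, and that the synopsis makes no claim of external validation. The choice of stability index does belong in a SAP. But the words in Table 3a state a property of the primary outcome that the described design lacks, and the difference from the synopsis is itself something to reconcile.

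**Conclusion.** The point holds for the label in both Table 3a rows. As described, the study can offer internal validation or construct validity of its endotypes, not external validation. This rests on the absence of any independent cohort or hold-out in the protocol; if one exists, naming it would answer the point. That site-driven classes could pass the check is a possibility the design leaves open, not a predicted result.

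The secondary part is narrower. Up to 72 hours plasma supports no trajectory, and up to Day 7 at most a straight line. The same is true of required imaging under Table 5a, subject to the differing schedules in the synopsis and section 2.1. What changes is what the primary outcome may claim; no sample size or effect estimate is affected.

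**What to change.** In both Table 3a rows, do one of the following:

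- Replace external validation with internal validation of the latent classes by (a) bootstrap class stability and (b) leave-one-site-out replication: fit in all sites but one, assign infants in the site left out, and compare class profiles and prevalence. With five sites at most, this gives at most five folds.
- Name an independent cohort, or a prespecified site or temporal hold-out.

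In addition:

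- Keep trajectory modelling in either row only as a descriptive or construct-validity analysis of named measures with at least three time points. Plasma does not qualify. Apply the same rule at 72 hours and at Day 7.
- Unless an independent cohort is named, state that external validation awaits one.
- Reconcile Table 3a with the synopsis outcome and the phenotyping methods in section 11.2, and reconcile the early imaging times across the synopsis, section 2.1, section 6.2.4 and Table 5a.

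The internal-validation route costs wording and analysis time, with no new infants, samples or visits. The claim becomes weaker, and small classes may not replicate when a site is left out: if sites were of equal size (an assumption), each fold would test about 550 / 5 = 110 infants.
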